Thermoregulation and Cognition During Cool Ambient Exposure in Tetraplegia

NCT02379156

Most Recent Update / Human Subjects Protection Review Board Approval: 03/07/2023

RESEARCH PROTOCOL

1. SPECIFIC AIMS.

Problem Statement: After a cervical spinal cord injury (SCI) the motor, sensory and autonomic deficits cause, among other detriments, a blunted ability to maintain a constant core body temperature (Tcore). Impaired thermoregulation leaves persons with tetraplegia more susceptible to hypothermia than able-bodied persons (AB). In addition, the commonly prescribed medications to treat the spasticity, pain, and depression that accompany this injury, raise the vulnerability of this population to hypothermia, and its potentially fatal consequences.

Persons with tetraplegia are routinely exposed to cool ambient temperatures in their homes, work environments, and while waiting on or riding in accessible public transportation. The thermoregulatory response and cognitive consequences of prolonged exposure to cool temperatures have not been investigated in persons with tetraplegia. Preliminary data has suggested that even limited exposure to cool temperatures can cause a drift in Tcore to values approaching hypothermia. With this lowering of Tcore, cognitive performance may also be negatively affected. Such demonstration of mild (or worse) hypothermia and concomitant declines in cognitive function would warrant investigations of interventions to mitigate this drift in persons with tetraplegia. The International Spinal Cord Injury Skin and Thermoregulation Basic Data Set is further evidence of the growing recognition that many people with SCI are affected by thermoregulatory dysfunction.

There has been a paucity of work addressing the thermoregulatory responses of persons with SCI to cool ambient temperatures, and even less study of medical interventions to improve maintenance of Tcore. Although it is presently unknown as to whether a modest fall in Tcore impairs cognition in persons with SCI, one may expect deterioration in cognitive function because central neurological function is exquisitely temperature sensitive. As such, cognitive performance will be determined after decrement in core body temperature.

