The goals of this study are: 1) to improve our understanding of the thermoregulatory mechanisms of individuals with tetraplegia when exposed to cold, 2) to determine if cognitive performance is affected after a decrement in Tcore, and 3) to determine if administration of an alpha-adrenergic agonist (midodrine) delays or decreases the expected downward drift in Tcore and possible deterioration of cognitive performance.

In order to address our goals, we have designed a study methodology which consists of comparing the physiological and subjective responses of the two study groups (tetraplegia versus AB controls) from thermoneutral (27°C) to cool (18°C) environments in the seated position. On a 2nd visit, the subjects with tetraplegia who completed the first visit, will be given midodrine while seated prior to being placed in the cool environment to compare their responses with midodrine to their responses to the identical challenge without midodrine.

Overall Objective: The overall objective is to identify and address the physiological and cognitive problems that persons with spinal cord injury (SCI) face when exposed to routinely encountered cool temperatures.

- Specific Aims: during exposure to a cool environment (18°C) for up to 120 min in the seated position:

Primary Specific Aim: To determine the change in: (1) Tcore and to assess (2) cognitive performance (attention, processing speed, working memory, and executive function) before and

after exposure to cool temperatures. **Primary Hypotheses:** Based on our pilot data: (1) Sixty-six percent of persons with tetraplegia and none of the controls will demonstrate a decline of 1.0°C in Tcore; (2) Eighty percent of persons with tetraplegia and 30% of controls will have a decline of at least one T-score in Stroop Interference scores (a measure of executive function).

Secondary Specific Aims: To determine the change in: (1) the average of distal skin temperatures, (2) metabolic rate, and (3) subjective rating of thermal sensitivity. **Secondary Hypotheses:** Persons with tetraplegia will have less of a percent change in average distal skin temperatures and metabolic rate, and report blunted thermal sensitivity ratings compared with able-bodied (AB) controls.

Tertiary Specific Aim: To determine if a 10 mg dose of midodrine will (1) reduce the decrease in Tcore and (2) prevent or delay the decline in cognitive performance in the group with tetraplegia.

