Tertiary Hypothesis: Because the one-time, off-label use of midodrine will address the primary systemic impairment to cold exposure in persons with tetraplegia, lack of peripheral vasoconstriction, the induced vasoconstriction will serve to reduce cutaneous heat losses and will be anticipated to blunt the decrease in Tcore and delay the decline in cognitive performance compared to cool exposure without drug administration.

METHODS

Research Design and Methods: A prospective, two-group comparative study will be performed to determine the effects of cold thermal challenge on Tcore, cognitive performance, distal skin temperatures (Tsk), metabolic rate (VO₂), and thermal sensitivity (TS) in the seated position in individuals with tetraplegia and in a matched AB control group (Visit 1). During Visit 2, a prospective, within-group comparative study will be performed to determine the effects of cold thermal challenge on Tcore, cognitive performance, Tsk, VO₂, and TS only in individuals with tetraplegia after midodrine administration compared to their response on Visit 1.

A prospective, two-group comparative study will be performed to determine the effects of cold thermal challenges on core temperature measured by rectal thermocouple (Tre), skin temperature by surface thermocouples (Tsk), cognitive performance by [digit span section of the Wechsler Adult Intelligence Scale-Fourth Edition (WAIS-IV), Stroop Color and Word tests, Symbol Digit Modalities Test (SDMT), memory and delayed recall sections of the Montreal Cognitive Assessment (MoCA)], metabolic rate measured by oxygen consumption (VO₂), and thermal sensation by the thermosensitivity cold scale in the seated position in individuals with tetraplegia and in a matched AB control group (Visit 1). During Visit 2 a prospective, within-group comparative study will be performed to determine the effects of thermal challenge on Tcore, skin temperature, cognitive performance, metabolic rate, and thermal sensation in individuals with tetraplegia who have participated in Visit 1 and in those same individuals who repeat the Visit 1 challenge identically, except for the administration of midodrine prior to the cold challenge while in the seated position (Visit 2).

Subjects: Fifteen subjects with tetraplegia (C4-T1) and 15 non-SCI control subjects matched for age (\pm 5 years), and gender will be recruited for study.

Subject Recruitment:

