Patients referred by their physician following routine physical examinations will be approached for possible study enrollment. Physicians will be informed of the inclusion and exclusion criteria for this study and will be able to provide us with the assurance that the patient is an appropriate study subject and that they were willing to speak with the study coordinators.

Veterans with SCI responding to IRB approved articles in lay publications and advertisements. Veterans with an ongoing relationship with our center, such as through attendance at one of the following SCI clinics: (1) Metabolic, (2) Pulmonary, or (3) GI.

a. Inclusion criteria

1. Between 18 and 68 years of age;
2. Duration of injury \geq 1 year;
3. Level of SCI C4-T1; (AIS A & B)
4. Euhydration (Subjects will be instructed to avoid caffeine and alcohol, maintain normal salt and water intake, and avoid strenuous exercise for 24 hours prior to study); and
5. Age (\pm 5 years) and gender matched AB control group.

b. Exclusion criteria

1. Evidence of sympathetic integrity below the lesion level by the skin axon-reflex vasodilatation (SkARV) test (a distinctly diminished vasodilatory response to mechanical stimulation of the skin is evident below the lesion level when sympathetic integrity has been interrupted);
2. Known allergies to midodrine hydrochloride;

Exclusion Criteria shared by subjects with SCI and AB controls

3. PMH of diagnosed heart, kidney, peripheral vascular, or cerebral vascular disease, or diabetes mellitus;
4. Hypertension (BP>140/90 mmHg);
5. Untreated thyroid disease;
6. Acute illness or infection;
7. Current smoker;
8. Pregnancy.

Preparation for Study Visits: AB controls will be gender- and age-matched (\pm 5 years) to subjects with SCI. All subjects will be instructed to avoid caffeine and alcohol, maintain normal salt and water intake, and avoid strenuous exercise for 24 hours prior to study to ensure euhydration. Subjects will enter the laboratory between 8:00-10:00 AM on each study visit. Study visits will be separated by a minimum of 1 day and no more than 14 days. Subjects will wear minimal clothing (gym shorts, sports bra) during the study to maximize skin exposure to the cool temperature. Each subject will be asked to eat a light, standard meal (plain bagel or 2 pieces of toast) 2 hours prior to their visit. Subjects will be asked to empty their bladders prior to each study visit and again upon arrival, if needed.

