Thermal Challenge: Following completion of the BL period, subjects will be wheeled into an 18°C thermal chamber for 120 minutes or until Tcore ≤ 35°C. Tcore, Tsk, and VO₂ will be continuously monitored to ensure subject safety throughout the protocol; brachial BP, HR, blood oxygen saturation, TS, and symptoms of autonomic dysreflexia and hypothermia will be assessed at 10-minute intervals while LDF will be measured for 5 minutes every 20 minutes. Venous blood will be collected at 50-minute intervals. After 1 hour of Cold Challenge, hypertonicity (spasticity) will be measured again only in subjects with tetraplegia in both upper extremities, at the elbows and wrists (flexors and extensors) and both lower extremities, at the knees and ankles (flexors and extensors) using the Modified Ashworth Scale. A decrease in Tcore to ≤ 35°C, or subject discomfort, will result in termination of the protocol. The cognitive performance battery will be administered when Tcore has declined 1°C or is ≤ 35.5°C (in subjects with tetraplegia) or after 120 minutes of cold exposure (in both groups) on Visits 1 & 2.

Visit 2: Cold Ambient Challenge with Midodrine: Visit 2 will be completed in subjects with tetraplegia who participated in Visit 1 and who had an impaired ability to maintain Tcore. Following completion of the BL period, hypertonicity (spasticity) will be measured only in subjects with tetraplegia in both upper extremities, at the elbows and wrists (flexors and extensors) and both lower extremities, at the knees and ankles (flexors and extensors) using the Modified Ashworth Scale. Subjects will then be orally administered midodrine hydrochloride (10 mg). Forty minutes after midodrine administration (for onset of drug effect), a second BL collection will be obtained, and hypertonicity (spasticity) will again be measured only in subjects with tetraplegia in both upper and lower extremities. Subjects will then be wheeled into the 18°C thermal chamber for 120 minutes or until Tcore ≤ 35°C. Data collection will follow the same schedule and be conducted in the seated position as in Visit 1. After 1 hour of Cold Challenge, hypertonicity (spasticity) will again be measured in both upper and lower extremities.

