Statistical Analyses: *Visit 1:* Depending on the data distribution, parametric or non-parametric analyses will be performed. For the within-group comparisons, paired-t and Wilcoxon signed rank tests will be conducted to determine intra-group differences in the dependent variables. For the between-group comparisons, unpaired-t and Mann-Whitney U tests will be performed to determine between-group differences in the percentage change (from thermoneutral to cool) of the dependent variables (Tcore, cognitive performance, Tsk, and VO₂).

Visit 2 (with midodrine): Depending on the data distribution, parametric or non-parametric analyses will be performed. Within the group with tetraplegia, paired-t or Wilcoxon signed rank tests will be used to determine differences in the percentage change (from thermoneutral to cool) of the dependent variables (Tcore, cognitive performance, Tsk, VO₂), without midodrine (Visit 1) compared to with midodrine (Visit 2).

Sample size: The primary outcome variables are Tcore and cognitive performance. For Tcore, using our preliminary data obtained post cold exposure in tetraplegic and AB subjects, mean Tcores of $35.95 \pm 0.63^\circ\text{C}$ and $37.3 \pm 0.28^\circ\text{C}$ were demonstrated, respectively. The difference between the groups for these values yields a power of 99.9% at an alpha of 0.05 with 8 subjects

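### Visit 2 entry carries an undefined condition on holding core temperature; if it is judged on the Visit 1 response and excludes anyone, regression to the mean favours midodrine in the paired Tcore test

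*Combined protocol and SAP*

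**What the plan says.** Three places in the combined protocol and SAP say who takes part in Visit 2.

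- **Specific Aims (goals and methodology):** "the subjects with tetraplegia who completed the first visit, will be given midodrine while seated prior to being placed in the cool environment". There is no Tcore condition.
- **Research Design and Methods:** the effects are studied "in individuals with tetraplegia who have participated in Visit 1 and in those same individuals who repeat the Visit 1 challenge identically", apart from the drug. Again there is no Tcore condition.
- **Visit 2 section of the Methods:** the procedures there open with a narrower statement: "Visit 2 will be completed in subjects with tetraplegia who participated in Visit 1 and who had an impaired ability to maintain Tcore". No size of fall, absolute value, time point or assessor is given.

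For the analysis, Statistical Analyses (Visit 2) plans a paired t-test or its Wilcoxon counterpart, depending on the distribution; these "will be used to determine differences in the percentage change (from thermoneutral to cool) of the dependent variables", and the contrast is "without midodrine (Visit 1) compared to with midodrine (Visit 2"). Visit 1 is therefore the only control for midodrine.

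Two other statements bear on how the condition should be read. The Problem Statement attributes to cervical injury in general "a blunted ability to maintain a constant core body temperature (Tcore"). The exclusion criteria already remove subjects with "Evidence of sympathetic integrity below the lesion level by the skin axon-reflex vasodilatation (SkARV) test".

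**The concern.** The condition is joined to Visit 1 participation and put in the past tense, in the sentence that decides who does Visit 2. The more natural reading is a rule judged on how the subject's Tcore behaved at Visit 1. On the plan's own expectation that 66% will fall by 1.0°C, such a rule could exclude a material share of the group.

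A subject's Visit 1 fall is partly stable and partly specific to that day. Choosing subjects because the fall was large also chooses days on which it happened to be large. At Visit 2 the day-specific part averages out, and the fall is smaller whether or not the drug works. This is the pattern that the tertiary hypothesis predicts for midodrine, and nothing in the planned paired test separates the two. An apparent effect on Tcore could then be partly or wholly an artefact of selection. As written, the Visit 2 population also cannot be reproduced by a second team.

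**Working it through.** **1. Plan's own figures.** The plan gives no sample size or power for Visit 2. Its Visit 1 power for 66% versus 0%, 15 per group, reproduces with the pooled-variance formula. The mean proportion is 0.33 and the null SE is √(2 × 0.33 × 0.67/15) = 0.172. The alternative SE is √(0.66 × 0.34/15) = 0.122, so (0.66 − 1.96 × 0.172)/0.122 ≈ 2.64 and power is 99.59%, as stated. The Stroop figure (82.75%) also reproduces. Neither depends on who enters Visit 2.

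**2. Inputs.**
- From the documents: 15 subjects with tetraplegia; 66% expected to fall 1.0°C (4 of 6 in the pilot fell at least that much); post-cold Tcore 35.95 ± 0.63°C; largest control fall 0.297°C.
- Possible benchmarks for the condition: a 1.0°C fall (Sample size, and the Thermal Challenge section, which times the cognitive battery by a 1°C decline or Tcore ≤ 35.5°C), or a fall beyond the control range, about 0.3°C. The documents tie neither to Visit 2 entry.
- Assumed: the cut-off; normally distributed falls; SD of the fall 0.63°C, borrowed from post-cold Tcore; between-visit correlation ρ of 0.3 to 0.9; an inert drug.

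**3. Closed form.** If 66% exceed 1.0°C, the mean fall is 1 + 0.412 × 0.63 = 1.26°C. For cut-off c, the expected Visit 1 minus Visit 2 difference among those selected is

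bias = (1 − ρ) × SD × φ(z)/P(selected), with z = (1.26 − c)/SD.

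- c = 1.0°C: z = 0.412, φ = 0.366, P = 0.66. Then 0.63 × 0.366/0.66 = 0.350, and multiplying by 0.7, 0.5, 0.3 and 0.1 gives 0.245, 0.175, 0.105 and 0.035°C.
- c = 0.3°C: z = 1.52, φ = 0.125, P = 0.936. Then 0.63 × 0.125/0.936 = 0.084, giving 0.059°C at ρ = 0.3 and 0.008°C at ρ = 0.9.
- Nobody excluded, or ρ = 1: zero.

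**4. Simulated two-sided 5% paired t-test** (15 subjects before selection, ρ from 0.3 to 0.9):

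| Rule | Apparent benefit | Total rejection | In favour of midodrine (nominal 2.5%) |
|---|---|---|---|
| Fall ≥ 1.0°C | 0.24 to 0.04°C | 18.0 to 6.3% | 17.8 to 5.3% |
| Fall ≥ 0.3°C | 0.06 to 0.01°C | 5.7 to 5.2% | 4.6 to 3.1% |
| Nobody excluded | 0°C | about 5% | about 2.5% |

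Repeat runs agree to within a few tenths of a percentage point. Modelling the stop at 35°C matters little: at 1.0°C the rate in favour is 18.0 to 5.5% with it and 17.2 to 5.3% without. On the plan's percentage scale, with a common baseline of 35.95 + 1.26 = 37.21°C, the 1.0°C bias is 0.24/37.21 to 0.035/37.21, or about 0.65 to 0.09 percentage points.

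**5. Chance that the rule excludes nobody.** 0.66^15 = 0.002 at 1.0°C; 0.936^15 ≈ 0.37 at 0.3°C. Expected numbers selected are 15 × 0.66 = 9.9 and 15 × 0.936 = 14.0.

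**The case against.** The strongest reply is that the phrase merely describes the condition: thermoregulation is impaired in tetraplegia as a group, and sympathetic integrity is already an exclusion. On that reading nobody is left out and the paired test is unbiased. The documents do not rule this out, so a reader who infers that the plan certainly biases the midodrine result goes too far. Against it, the phrase would then add nothing to the sentence it stands in.

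Second, the size rests on inputs that the documents do not give. This stands. The 18% needs a correlation of 0.3, while the plan standardises time of day, meal and hydration and keeps visits within 14 days, which may make falls more repeatable. The excess is clear only at a strict cut-off. With the Wilcoxon test, which the plan also allows, the rate in favour at 1.0°C is about 15% (ρ = 0.3) to 4% (ρ = 0.9).

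Third, restricting Visit 2 to subjects who lose heat is a defensible enrichment choice. That is so, but enrichment does not require the selecting measurement to be the comparator without adjustment.

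A reader might also infer an opposite bias from the goals, which refer to completing Visit 1, since a Tcore of 35°C or less "or subject discomfort, will result in termination of the protocol". The documents do not support giving this equal weight. The Thermal Challenge section defines the exposure as lasting 120 minutes or until Tcore reaches 35°C, so reaching that value is a planned end of the challenge. The effect would also be trivial: 0.005 to 0.044°C, with total rejection of 5.2 to 5.8%.

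**Conclusion.** The concern holds in conditional form. It is certain that the Visit 2 section adds an undefined condition that the goals and the design lack. If that condition is an entry rule judged on the Visit 1 Tcore response and it excludes anyone, the planned paired Tcore test is biased towards midodrine. The bias runs from negligible (lenient cut-off, high correlation) to about 0.24°C with total rejection of 18% (1.0°C cut-off, correlation 0.3), under the assumed SD, normality and inert drug. If the phrase is descriptive, there is no such bias.

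The scope is the tertiary Tcore comparison. Cognition, skin temperature and VO₂ are touched only as far as their Visit 1 errors correlate with those of Tcore. The Visit 1 group comparisons and the stated power are unaffected. Giving midodrine always second and without placebo is a separate limit on the midodrine conclusion, which remains whichever way this point is settled. This should be fixed; confidence is medium because the reading is open.

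**What to change.** The sponsor should reconcile the Specific Aims, the Research Design and the Visit 2 section on who enters Visit 2, and say whether the impairment phrase is an entry rule or a description. Which entry rule is right is not for this review. The analysis follows from the answer.

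- **Entry does not depend on the Visit 1 Tcore response:** keep the planned paired test on all who attend Visit 2.
- **The condition stays as an entry rule:** fix its definition, in terms of recorded Visit 1 data, before those data are seen. For Tcore, replace the paired test with a likelihood-based repeated-measures model with unstructured covariance that includes the Visit 1 values of all subjects with tetraplegia, including those not selected. Selection then depends only on observed data in the model, and nearly all the bias goes: the mean bias stays below 0.01°C in simulation at a 1.0°C cut-off, against 0.24 to 0.04°C for the paired test. Report the paired test in selected subjects as secondary and subject to regression to the mean.

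In both cases, state the fixed order and lack of placebo as limits.

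The cost is a short wording amendment and, in the second case, a little more analysis work. The model gives wider intervals, and it relies on a linear relation between visits estimated from few subjects and extended to those who did not attend Visit 2.

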per group (double-sided). Four of the 6 subjects with tetraplegia (66%) had a decrease of $\geq 1.0^{\circ}\text{C}$ while no control demonstrated a decline $> 0.297^{\circ}\text{C}$ in Tcore (0%). Cognitive performance will be assessed after a Tcore decline of 1.0°C in subjects with tetraplegia. Using 66% (tetraplegia) versus 0% (control) with a count of 15 per group, the power is 99.59% at an alpha of 0.05. We are hypothesizing that 66% of subjects in the SCI group will have a decline of 1.0°C in Tcore while none of the controls will demonstrate the same decline. We are well-powered to test this endpoint. For cognitive performance, preliminary data indicated that 5 of 6 subjects with tetraplegia (83%), compared to 2 of 6 AB subjects (33%), demonstrated a decline of ≥ 1 T-score in Stroop Interference scores post cold exposure. Using 83% (tetraplegia) versus 33% (control) with a count of 15 per group, the power is 82.75% at an alpha of 0.05 (double-sided).⁷⁶ We hypothesize that 80% of subjects in the SCI group will have a decline of at least 1 T-score in Stroop Interference scores while 30% of controls will demonstrate that same decline. We are well-powered to test this outcome.

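### The Stroop primary hypothesis and its 82.75% power compare two proportions, but the planned between-group tests compare percentage change

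*Combined protocol and SAP*

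**What the plan says.** **Hypotheses.** Specific Aims, Primary Hypotheses, states both as shares of subjects passing a threshold. For core temperature (a fall of 1.0°C): "Sixty-six percent of persons with tetraplegia and none of the controls will demonstrate a decline". For cognition: "Eighty percent of persons with tetraplegia and 30% of controls will have a decline of at least one T-score in Stroop Interference scores". The Sample size section repeats the second: "We hypothesize that 80% of subjects in the SCI group will have a decline of at least 1 T-score in Stroop Interference scores".

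**Analysis.** For Visit 1 the Statistical Analyses section says "Depending on the data distribution, parametric or non-parametric analyses will be performed", and between groups "unpaired-t and Mann-Whitney U tests will be performed to determine between-group differences in the percentage change". Within groups it plans paired t and Wilcoxon signed rank tests. It names no test of proportions and defines no responder variable for analysis.

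**Power.** The Sample size section says "The primary outcome variables are Tcore and cognitive performance". For core temperature it gives two powers: 99.9% with 8 per group, from mean values after exposure (35.95, SD 0.63, against 37.3, SD 0.28), and 99.59% with 15 per group, from 66% against 0%. For Stroop it gives one: "Using 83% (tetraplegia) versus 33% (control) with a count of 15 per group, the power is 82.75% at an alpha of 0.05", two-sided. It concludes "We are well-powered to test this outcome".

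**The concern.** The share of subjects who pass a threshold and the average percentage change are different quantities. A significant difference in percentage change would not show that 80% and 30% of subjects passed the Stroop threshold. Nor would a clear difference in those shares guarantee a significant t or Mann-Whitney result. Followed exactly, the plan never tests the Stroop hypothesis in the form in which it is stated.

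The justification of the sample size has the same gap. The assurance of adequate power for Stroop rests on a figure for an analysis that is not planned, and the section gives nothing from which the power of the planned analysis could be worked out. If both kinds of result are later available and disagree, the protocol does not clearly say which one decides the hypothesis. A choice made after seeing the data would then be open to challenge.

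**Working it through.** **1. What the stated powers are.** Inputs from the Sample size section: n = 15 per group, alpha 0.05 (two-sided), p1 = 0.83, p2 = 0.33. The two-proportion z formula, with pooled variance under the null and no continuity correction, is

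power = Φ{[(p1 − p2) − 1.96·√(2p̄(1−p̄)/n)] / √[(p1(1−p1) + p2(1−p2))/n]}, with p̄ = (p1 + p2)/2.

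- 83% v 33%: p̄ = 0.58; null SE 0.1802; alternative SE 0.1554; (0.50 − 0.3532)/0.1554 = 0.945; Φ = 0.8275. This is the stated 82.75%.
- 66% v 0%: p̄ = 0.33; null SE 0.1717; alternative SE 0.1223; (0.66 − 0.3365)/0.1223 = 2.645; Φ = 0.9959. This is the stated 99.59%.

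Both 15-per-group figures are therefore correct as powers of a comparison of two proportions.

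**2. At the hypothesised Stroop rates.** 80% v 30%: p̄ = 0.55; null SE 0.1817; alternative SE 0.1571; (0.50 − 0.3560)/0.1571 = 0.917; Φ = 0.820. Using the pilot rates instead of the hypothesised ones raised the figure by about 0.7 points.

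**3. What a named two-proportion test would give.** Exact enumeration of all 16 × 16 outcomes, 15 per group, two-sided 0.05; size is the maximum over common rates.

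| Test | Stroop 80/30 | Tcore 66/0 | Maximum size |
|---|---|---|---|
| Boschloo or Barnard | 80.7% | 99.96% | 4.3% |
| Uncorrected chi-square | 81.5% | 99.96% | 5.5% |
| Fisher | 68.0% | 99.8% | 1.8% |

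For Stroop the choice of test matters. For core temperature it does not.

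**4. Core temperature on the continuous scale.** Pooled SD = √[(0.63² + 0.28²)/2] = 0.487; d = 1.35/0.487 = 2.77. The noncentral t power with 8 per group is 0.9992, which reproduces the stated 99.9%. This uses values after exposure, whereas the planned test uses percentage change, for which no SD is given. High power for that test is a reasonable inference, not a calculation from the documents.

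**5. Stroop on the continuous scale.** The documents give no mean or SD of change, so power cannot be computed from them. Two illustrations follow.

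- *By standardised difference.* A t-test with 15 per group needs d of about 1.06 for 80% power. Assumed values of d = 0.5, 0.8, 1.0 and 1.25 give 26%, 56%, 75% and 91%.
- *By the hypothesised shares.* If changes are normal with equal SDs, 80/30 implies d = z(0.80) − z(0.30) = 0.842 + 0.524 = 1.366, and a t-test power of 95%. A simulation of percentage change also fixed 80/30. It assumed a baseline T-score of 50 (SD 5 or 10), a larger change SD of 2, 5 or 8, and Mann-Whitney when Shapiro-Wilk p < 0.05 in either group. It gave 79% to 95% over SD ratios (tetraplegia to control) of 1/3, 1, 2.25 and 3, and about 84% with heavy tails (t, 3 df). With Mann-Whitney always used, it gave 76% to 94%, and about 85% with heavy tails.

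These scenarios show that the planned test could have power above or below 82.75%. They do not locate the trial's power.

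**The case against.** The strongest defence is that the planned tests fit the aim. The Primary Specific Aim is to determine change in core temperature and to assess cognition before and after exposure, the primary outcome variables are named as those two measures, and one family of between-group tests is specified for them. The percentages are introduced as based on pilot data and can be read as predictions. Much of this stands, and it is why keeping the continuous comparison is the smaller repair. It does not settle the matter, because the Sample size section states the responder percentages and then says that the trial is well powered to test them.

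It can also be said that the demonstrated effect is small. That is fair: moving to the hypothesised rates costs 0.7 points, and a size-controlling exact test gives about 81%. A continuous comparison often has more power than a dichotomised one.

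A reader might infer that the trial is underpowered for Stroop, or might take Fisher's 68% as its power. The documents support neither. Fisher's test is not planned, and the power of the planned test is unknown, not shown to be low. Preferring Boschloo or Barnard to another two-proportion test is partly a matter of taste; naming any one test would remove the mismatch.

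**Conclusion.** The point holds for Stroop as a mismatch between the hypothesis, the power figure and the analysis. The 82.75% is arithmetically right, but for an unplanned test and at 83/33, not 80/30. The corresponding figure at the hypothesised rates is 82.0% by the same formula, or about 81% with an exact test that holds its size. These figures rest on 15 evaluable subjects per group and two-sided 0.05. The power of the planned Stroop comparison cannot be stated from the documents.

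The same mismatch applies to core temperature, and a reader might infer that this endpoint is in jeopardy too. The figures do not support that: two-proportion power at 66/0 exceeds 99% even with Fisher's test, and the comparison of values after exposure has 99.9% with 8 per group. The one caveat is that high power for percentage change is inferred.

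This should be fixed as a matter of alignment and documentation. It does not call for a larger trial.

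**What to change.** Choose one of the following before the between-group data are analysed, and use the same wording in Primary Hypotheses, Statistical Analyses and Sample size.

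- **Keep the continuous comparison (the smaller change).** State that the t/Mann-Whitney comparison of change is the primary between-group test. Restate both primary hypotheses as between-group differences in change, with the responder percentages as descriptive predictions. Replace 82.75% with a power from the pilot mean and SD of Stroop change, or say that none can be given. *Cost:* wording, and those pilot summaries. The Sample size section shows only counts (5 of 6 and 2 of 6), so their availability is not known.
- **Test the responder hypotheses.** Add a named two-proportion test as the test of these hypotheses, and make the comparisons of change supportive. Restate the Stroop power at 80/30 for that test: about 81% for Boschloo's or Barnard's, which hold their size, or about 68% for Fisher's, in which case the claim of being well powered would need revision. *Cost:* wording, a lower stated power, and a primary test that is likely less powerful than the continuous comparison.

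Neither option adds subjects, visits or measurements.
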